7.6 Interim Analyses

There is no planned interim analysis.

7.7 Additional Analysis/Inference for US FDA

Analyses are as described in all preceding sections except for the items described below.

7.7.1 Primary Efficacy Analyses

There are 2 co-primary endpoints: the average grade change from baseline in the MAS-B ankle score at weeks 4 and 6 and the CGI by Physician at weeks 4 and 6. For both the co-primary endpoints, the statistical null hypothesis is that both the higher dose (8 U/kg) and the lower dose (4 U/kg) have the same mean as placebo. The alternative hypothesis is that at least one study dose has a different mean than placebo.

In addition to the primary statistical analyses cited in Section 7.3.1 for the average of the observed grade change from baseline in MAS-B, the average observed CGI by Physician at weeks 4 and 6 will also be analyzed using the same statistical method (with the same MMRM model).

The Hochberg procedure ([Hochberg and Tamhane, 1987](#)) will be used to control the family-wise type I error rate. With 2 doses and 2 co-primary endpoints in each dose, the maximum p value for the 2 co-primary endpoints in each dose will be used in the Hochberg procedure. We first define the following values:

- p11: p value for Botox 8 U/kg vs placebo comparing MAS-B
- p12: p value for Botox 4 U/kg vs placebo comparing MAS-B
- p21: p value for Botox 8 U/kg vs placebo comparing CGI
- p22: p value for Botox 4 U/kg vs placebo comparing CGI
- p1 = max(p11, p21), p2 = max(p12, p22).

p1 and p2 will be sorted in an increasing order to get $p(1) \leq p(2)$. The following decision rule will then be applied:

Step 1: If $p(2) \leq 0.05$, both doses are considered efficacious; otherwise go to step 2.

Step 2: If $p(1) \leq 0.025$, its corresponding dose is considered efficacious; otherwise go to step 3.

Step 3: Neither dose is considered efficacious.

For sensitivity analysis purposes to supplement the co-primary analyses, ANCOVA using MI for missing values will be conducted for the co-primary endpoints of MAS-B and CGI. The model will include baseline MAS-B as a covariate and factors of age group, treatment group, study center, and previous botulinum toxin exposure. A summary of the percentages of missing MAS-B and CGI scores by visit will also be provided. Additional sensitivity analyses for the MAS-B changes from baseline and CGI scores at each assessment time point will also be performed using ANCOVA with observed data, and linear contrasts will be used to estimate the treatment differences between each study dose and placebo. The secondary efficacy analyses will be the same as the statistical analyses cited in Section 7.3.2 except for the analyses for CGI by Physician which is described above.

8. Study Visit Schedule and Procedures

Please see Table 1 for a schematic of the schedule of visits and procedures.

8.1 Patient Entry Procedures

8.1.1 Overview of Entry Procedures

Prospective patients as defined by the criteria in Sections [4.3](#) and [4.4](#) (inclusion/exclusion criteria) will be considered for entry into this study.

8.1.2 Informed Consent and Patient Privacy

The study will be discussed with the patient/legally authorized representative and a patient/wishing to participate or his/her legally authorized representative must give informed consent and, when applicable, minor assent prior to any study-related procedures or change in treatment. The patient/legally authorized representative must also give authorization (US only), data protection consent (Europe only), and other written documentation in accordance with the relevant country and local privacy requirements (where applicable) prior to any study-related procedures or change in treatment.

Further information is provided in Section [10.1](#).

Each patient who provides informed consent and/or assent will be assigned a patient number that will be used on patient documentation throughout the study.

8.2 Procedures for Final Study Entry

At visit 3 (randomization) patients must meet all of the inclusion criteria and must not meet any of the exclusion criteria. Also, all females of childbearing potential must have a negative urine pregnancy test.

The patient is considered to have entered this study at the time of randomization to treatment on day 1. See Section 5.5 for the method for assignment to treatment groups/randomization.

8.3 Visits and Associated Procedures

Ideally, the CGI by Physician should be performed prior to administering the MAS-B and MTS to reduce the likelihood of the CGI being influenced by the spasticity evaluations. An alternative is to have different evaluators rate the CGI and perform the spasticity assessments (MAS-B and MTS). Whenever possible each procedure should be performed by the same evaluator for an individual patient throughout the trial. Study personnel should avoid

reviewing or discussing the MAS-B, MTS, or CGI scores from previous visits when they are completing these assessments.

In addition to the procedures outlined below, patients are to complete approximately 1-hour weekly standardized PT sessions (see Section 4.5.3) from week -2 through week 11.

8.3.1 Visit 1: 2 to 4 Weeks Before Day 1 (Screening)

- Obtain written informed consent and minor assent and data protection from the patient and/or legally authorized representative prior to performing any study-related procedures.
- Obtain patient identification number from the IVRS/IWRS.
- Obtain demographic information, including date of birth. Ensure that the patient will be \geq 2 years and \leq 16 years and 11 months (prior to 17th birthday) on projected day 1, randomization visit.
- Obtain medical and surgical history, ensuring that the patient is monoplegic or hemiplegic with dynamic muscle contracture of the ankle plantar flexors. Include details on histories of dysphagia, drooling, aspiration pneumonia, seizure, and epilepsy.
- Obtain past (in the last 3 months) and current concomitant medication use (including prescription, non-prescription, and herbal medications) and procedures. Previous use of botulinum toxin, phenol, and alcohol injections should be included.
- Perform C-SSRS (for patients \geq 6 years of age on day 1).
- Perform physical examination, including measurement of height and weight.
- Obtain vital signs (blood pressure, pulse rate, respiratory rate, and body temperature).
- Perform ECG.
- Collect blood sample for hematology, serum chemistry, and HbA1c analysis after informed consent is signed. Fasting blood samples should be collected unless the patient is not able to fast for approximately 8 hours. Patients who are willing to fast

and did not come to the visit in a fasting state may return prior to the day 1 visit for blood sample collection as long as the laboratory results can be received and reviewed at or before the day 1 visit.

- For patients who weigh at least 15 kg, collect blood sample for immunogenicity testing.
- Perform urine pregnancy test for all females of childbearing potential.
- Discuss choice of contraceptive method with female patients of childbearing potential and/or their caregivers and document method of contraception in the source documentation and the eCRF. Counsel such female patients/caregivers regarding the importance of maintaining their agreed upon method of contraception throughout the study.
- Ascertain spasticity only in the study lower limb using the HAT.
- Assess dystonia only in the study lower limb using the BAD scale.
- Assess gross motor function using the GMFCS-E&R.
- Assess spasticity in the ankle (with knee extended and knee flexed) and the knee of the study limb using the MAS-B.
- Perform MTS in the ankle of the study limb with knee extended and knee flexed. Note that the angle of slow stretch (R2) of MTS in the ankle with knee extended may be used to ensure the patient meets the inclusion criterion for acceptable minimal range of dorsiflexion.
- Evaluate inclusion and exclusion criteria.
 - For patients who are not eligible for the study (screen failures), depending on the reason(s) for screen failure, collect detailed information regarding spasticity, contracture, respiratory condition or functions associated with increased risk of aspiration, seizure, and epilepsy.
- Query patient for any adverse event that has occurred and any related medication used or procedure performed since signing the informed consent.

- Instruct patient/caregiver to initiate approximately 1-hour weekly standardized PT session with the therapist at week -2 and schedule through the last session at week 11.
- Schedule the next visit, if applicable.

8.3.2 Visit 2: Week -2 (PT Start) – Visit with the Physical Therapist

- Establish with each patient/caregiver 2 goals for the GAS (1 functional active and 1 functional passive) and define each level of patient-specific goal achievement for each of the 2 goals using the GAS by Physician.
- With the patient/caregiver, review protocol-specified standardized weekly PT and develop a patient-tailored PT plan.
- If patient reports adverse events to the therapist, the therapist should inform the Study Coordinator for further follow-up regarding adverse events and related medication used or procedures performed.
- Schedule the next weekly PT session.

8.3.3 Visit 3: Day 1 (Randomization/Treatment)

- **The following procedures must be performed prior to the study treatment:**
 - [REDACTED]
 - Note any update to medical and surgical history, if needed. Query patient/caregiver for any adverse events prior to study treatment.
 - Perform C-SSRS (for patients \geq 6 years of age at day 1).
 - For patients who are not eligible for the study (screen failures), depending on the reason(s) for screen failure, collect detailed information regarding spasticity, contracture, respiratory condition or functions associated with increased risk of aspiration, seizure, and epilepsy.
 - Obtain any update to concomitant medication use.
 - Obtain any information on new medical procedures or tests since the last visit.

- Obtain vital signs (blood pressure, pulse rate, respiratory rate, and body temperature).
- Obtain weight in kilograms.
- Review the results of the screening safety laboratory tests.
- Perform urine pregnancy test for all females of childbearing potential.
- Assess spasticity in the ankle (with knee extended and knee flexed) and the knee of the study limb using the MAS-B.
- Perform MTS for the ankle of the study limb with knee extended and knee flexed. Note that the angle of slow stretch (R2) of MTS in the ankle with knee extended may be used to ensure the patient meets the inclusion criterion for acceptable minimal range of dorsiflexion.
- Confirm the 2 goals selected and the definitions of patient-specific goal achievement using the GAS by Physician.
- [REDACTED]
- [REDACTED]
- [REDACTED]
- If applicable, counsel female patients and/or caregivers of childbearing potential regarding the importance of maintaining their agreed upon method of contraception throughout the study.
- Confirm patient continues to meet study inclusion and exclusion criteria.
- Calculate the dose for study treatment using the dose calculation worksheet and dose verification eCRF.
- Access the IVRS/IWRS to randomize the patient and obtain a study medication kit number.
- Inform IDR that patient is qualified for the study treatment and send blinded dosing summary to the IDR for study drug preparation.
- Inject assigned study treatment as per protocol (see Section 5.9).

- Query patient/caregiver for any adverse events and related medication used or procedure performed.
- Remind patient/caregiver of the importance of the weekly PT session.
- Schedule the next visit.

8.3.4 Visits 4, 5, 6, and 7: Weeks 2, 4, 6, and 8 (Follow-up Visits)

- [REDACTED]
- [REDACTED]
- [REDACTED]

- Query patient/caregiver for any adverse events.
- Perform C-SSRS (for patients \geq 6 years of age at day 1).
- Obtain any update to concomitant medication use.
- Obtain any information on new medical procedures or tests since the last visit.
- Rate the CGI by Physician before performing the spasticity assessments (MAS-B and MTS).
- Assess spasticity in the ankle (with knee extended and knee flexed) of the study limb using the MAS-B.
- Perform MTS for the ankle of the study limb with knee extended and knee flexed.
- Only at visit 7/week 8, evaluate the patient's performance for each of the 2 goals using the GAS by Physician.
- [REDACTED]
- [REDACTED]
- Remind patient/caregiver of the importance of the weekly PT session.

- Schedule the next visit.

8.3.5 Visit 8: Week 12 or Early Termination (Exit Visit)

- [REDACTED]
- [REDACTED]
- Query patient/caregiver for any adverse events.
- Perform C-SSRS (for patients \geq 6 years of age at day 1).
- Obtain any update to concomitant medication use.
- Obtain any information on new medical procedures or tests since the last visit.
- Perform physical examination, including measurement of weight.
- Obtain vital signs (blood pressure, pulse rate, respiratory rate, and body temperature).
- Collect blood sample for hematology, serum chemistry, and hemoglobin A1c analysis for all patients. Fasting blood samples should be collected unless the patient is not able to fast for approximately 8 hours.
- For patients who weighed at least 15 kg at the screening visit, collect blood sample for immunogenicity testing.
- Perform urine pregnancy test for all females of childbearing potential.
- Rate the CGI by Physician before performing the spasticity assessments (MAS-B and MTS).
- Assess spasticity in the ankle (with knee extended and knee flexed) of the study limb using the MAS-B.
- Perform MTS for the ankle of the study limb with knee extended and knee flexed.
- Evaluate the patient's performance for each of the 2 goals using the GAS by Physician.

- [REDACTED]
- [REDACTED]
- Any adverse event that is marked “ongoing” at the exit visit must be followed-up as appropriate.
- Enter patient exit status in the IVRS/IWRS.
- If the patient/legally authorized representative agrees to participate the follow on Study 191622-112 have the patient/legally authorized representative sign the consent/assent/privacy form and proceed with the day 1 visit for that study.

8.4 Instructions for the Patients

Patients/caregivers will be instructed to strictly follow the study visit schedule and report any changes in condition to the investigative site.

Patients/caregivers will be instructed to complete the approximately 1-hour weekly standardized PT sessions (see Section 4.5.3) from week -2 through week 11.

8.5 Unscheduled Visits

Unscheduled visits can be performed if safety concerns arise and at the discretion of the investigator. Additional examinations may be performed as necessary to ensure the safety and well being of patients during the study. eCRFs will be completed for each unscheduled visit.

8.6 Compliance With Protocol

At each post-baseline visit, patients/caregivers will be questioned on concomitant medication use and procedures or tests since the last visit to ensure protocol compliance.

8.7 Early Discontinuation of Patients

Patients may voluntarily withdraw from the study at any time or may be withdrawn at the discretion of the investigator and Allergan due to clinically significant findings including, but not limited to, adverse events and clinical laboratory abnormalities. Allergan will be notified of early patient discontinuation from the study and the reason for discontinuation will be clearly documented on the appropriate eCRF.

The last visit for the patient will be considered the study exit visit. Procedures for week 12 will be performed if the study exit visit occurs earlier than week 12.

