1.3 BOTOX for Management of Pediatric Spasticity

Botulinum neurotoxin type A (BoNT-A) blocks neuromuscular conduction by binding to receptor sites on motor nerve terminals, entering the nerve terminals, and inhibiting the release of acetylcholine. When injected intramuscularly at therapeutic doses, BoNT-A produces localized chemical denervation of the muscle, resulting in focal muscle weakness. This muscle weakness is reversible through nerve ending recovery over a period of 3 or more months. Relaxation of rigid muscles by BoNT-A allows a child to participate in PT or OT, which encourages the use of both targeted and antagonistic muscles with goals of muscle stretching, strengthening, improved motor control, and acquisition of new skills. There has been considerable experience worldwide since the early 1990s with the use of BOTOX in the treatment of spasticity associated with cerebral palsy.

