5.6 Treatment Regimen and Dosing

This study will include 1 treatment of the study limb.

The volume and corresponding dose for each identified muscle and the total dose will be calculated for each of the 3 potential treatment assignments to maintain blinding. A dosing summary will be provided to the IDR who will prepare the study medication according to the randomization assignment.

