8.8 Withdrawal Criteria

Patients have the right to withdraw from the study at any time and for any reason without prejudice to his or her future medical care by the physician or the institution. The investigator and Allergan also have the right to withdraw a patient from the study at any time for any reason. Patients who withdraw from the study will not be replaced.

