9.3 Procedures for Reporting a Serious Adverse Event

Any serious adverse event occurring during the study period (beginning with informed consent) and for at least 28 days after the last dose of study drug must be immediately reported no later than 24 hours after learning of a serious adverse event. Serious adverse events must be reported to Allergan or its designee as listed on the Allergan Study Contacts Page and recorded on the serious adverse event form. All patients with a serious adverse event must be followed and the outcomes reported. The investigator must supply Allergan and the IRB/IEC with any additional requested information (eg, autopsy reports and terminal medical reports).

In the event of a serious adverse event, the investigator must:

1. Notify Allergan immediately by fax or email using the serious adverse event form (contact details can be found on page 1 of the serious adverse event form); phone numbers and relevant Allergan personnel contacts are also on the front page of protocol.
2. Obtain and maintain in his/her files all pertinent medical records, information, and medical judgments from colleagues who assisted in the treatment and follow-up of the patient.
3. Provide Allergan with a complete, written case history (adverse event report form) which includes a statement as to whether the event was or was not related to the use of the investigational drug.
4. Promptly inform the governing IRB/IEC of the serious adverse event as required by the IRB/IEC, local regulations, and the governing health authorities.

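### Study drug is given once, on day 1, but a child withdrawn for an adverse event has no defined follow-up to week 12, so new SAEs and primary-endpoint visits can be missed unnecessarily

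*Protocol*

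**What the plan says.** **One injection.** Protocol 5.6: "This study will include 1 treatment of the study limb". Protocol 5.1 defines study treatment as BOTOX or placebo plus standardized physical therapy (PT), and 5.6.1 runs the weekly PT through week 11.

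**Withdrawal.** Under Protocol 8.7 patients "may be withdrawn at the discretion of the investigator and Allergan due to clinically significant findings including, but not limited to, adverse events" and laboratory abnormalities. Section 8.8 is wider: "The investigator and Allergan also have the right to withdraw a patient from the study at any time for any reason". Both sections concern leaving the study. Neither describes a child who stops an intervention and remains in follow-up.

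**What happens at exit.** Protocol 8.7: "The last visit for the patient will be considered the study exit visit", and "Procedures for week 12 will be performed if the study exit visit occurs earlier than week 12". Section 8.3.5 applies the same procedures to week 12 and to early termination.

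**What happens after exit.** Protocol 9.2 asks for AEs ongoing at exit to be followed as appropriate. Section 9.3 asks for patients with an SAE to be followed and outcomes reported. New SAEs that occur in the study period and "for at least 28 days after the last dose of study drug must be immediately reported".

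**Duration of effect.** Protocol 1.3 calls the muscle weakness "reversible through nerve ending recovery over a period of 3 or more months".

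**The concern.** Withdrawing a child after day 1 cannot undo the injection. It can end PT and lift the protocol's restrictions on other treatments, but neither step requires observation to stop. As written, a decision prompted by a safety finding also ends the remaining efficacy visits and the search for new events, while the drug effect described in the protocol may still be present.

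Two things are at stake. The first is safety capture. The SAP (6.2) screens 39 preferred terms for possible distant spread of toxin, and an event that starts after exit need not be captured unless it is serious and occurs by day 29. The second is missing data in the primary analysis, which could be related to outcome. This matters most for the CGI, co-primary for the US FDA, because Protocol 12.1.15 tells the rater to weigh side effects and adverse events. Withdrawal for an adverse event would then remove later scores for a reason that is part of the score.

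**Working it through.** The plan gives no figure for follow-up after withdrawal, so there is none to reproduce on this point. Its sample-size figures do reproduce: 117 per group, a difference of 0.35 and an SD of 0.75 give 94.5% power by the noncentral t (stated 94%). The fix leaves that calculation unchanged.

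**Inputs**

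- Day 1 is the treatment day, and post-treatment study day = visit date − day 1 date + 1 (SAP 2.2).
- Week 12 target is day 85 (SAP 2.2), so follow-up is 85 − 1 = 84 days.
- The SAE minimum is 28 days after the last dose (Protocol 9.3). With one dose on day 1 it ends on day 1 + 28 = day 29.
- Visit windows (SAP 2.2): week 2 is days 2–22, week 4 is days 23–36, week 6 is days 37–50.
- Assumption: for a withdrawn child the study period in 9.3 ends at the exit visit. Section 8.7 implies this; 9.3 does not define it.

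**Step 1: time without required capture of new events**

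New SAEs: uncovered days = 85 − max(exit day, 29). New non-serious AEs have no stated minimum after exit, so uncovered days = 85 − exit day. Shares are of 84 days.

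| Exit | New SAEs uncovered | New non-serious AEs uncovered |
|---|---|---|
| Week 2 (day 15) | 85 − 29 = 56 (67%) | 85 − 15 = 70 (83%) |
| Week 4 (day 29) | 85 − 29 = 56 (67%) | 85 − 29 = 56 (67%) |
| Week 6 (day 43) | 85 − 43 = 42 (50%) | 85 − 43 = 42 (50%) |
| Week 8 (day 57) | 85 − 57 = 28 (33%) | 85 − 57 = 28 (33%) |

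The 28-day clause helps children who leave before day 29 and adds nothing for later leavers.

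**Step 2: effect on the primary endpoint**

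The endpoint averages weeks 4 and 6. Exit-visit data are assigned by study day, not by the visit's label.

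- Exit on days 2–22: data fall in the week 2 window, so weeks 4 and 6 are both missing.
- Exit on days 23–36: the exit visit can supply week 4, and week 6 is missing.
- Exit on days 37–50: the exit visit can supply week 6.

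Only exits before day 23 lose both visits. The same rule places the exit blood sample of a day 15 leaver at week 2.

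**Step 3: how many children**

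The plan enrols 412 to obtain 351 completers: 412 − 351 = 61, and 61/412 = 14.8%. This is the allowance for non-completion from all causes. The documents do not say what part would be investigator or sponsor decisions prompted by clinical findings. Any share from none to all of the 61 fits the allowance, so no count is claimed.

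**The case against.** **Study treatment is not over on day 1.** A reader might infer that no treatment is left to stop and that withdrawal removes only data. The documents do not support that. PT is part of study treatment and runs through week 11, and Protocol 4.5.2 restricts casting, dynamic splints, other toxin and new anti-spastic drugs. Withdrawal ends all of this. The objection stands against that reading, but stopping PT does not require data collection to stop.

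**The exit visit recovers much.** Early leavers have MAS-B, CGI, laboratory, antibody and C-SSRS assessments at exit. This stands: those data are collected, only earlier. What is lost is later visits and new events.

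**The model copes with missing visits.** The primary MMRM uses observed data from weeks 2 to 12, with multiple imputation as a sensitivity analysis, and the exit CGI can already reflect the event that led to withdrawal. This reduces the problem. It does not show whether the child later improved or worsened, and adverse events are not in the model.

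**The 28-day clause is only a floor.** True. It extends capture for early leavers. The gap comes from ending observation at exit.

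**The rule is permissive and may seldom be used.** True. Section 8.7 allows withdrawal without requiring it, and 4.5.2 already lets children stay after a prohibited medication. The laboratory route is probably rare, since the only scheduled post-treatment blood sample is at exit.

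**Bias is not shown.** A reader might infer that the high-dose safety profile will look better than it is. The documents do not establish this. Site staff other than the drug reconstitutor are blinded, the event that prompts withdrawal is recorded, and the SAP lists AEs leading to discontinuation and tabulates reasons by group. Bias is possible, but neither its direction nor its size can be stated.

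**Conclusion.** The gap is real but limited. For a child withdrawn on or before day 29, 67% of planned follow-up has no required capture of new SAEs. The share is 50% at week 6 and 33% at week 8, so it exceeds half only for exits before week 6. Exits before day 23 lose both primary-endpoint visits. The missingness is avoidable and may be related to outcome, most plausibly for the CGI.

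This rests on reading the study period in 9.3 as ending at exit for a withdrawn child, and on nothing else in the documents requiring later contact; none was found beyond follow-up of ongoing AEs and known SAEs. The number of children affected is unknown, so no effect on power or on the treatment comparison is claimed. The point is a cheap improvement, not a flaw that invalidates the design.

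**What to change.** Reconcile Protocol 8.7, 8.8 and 9.3 together. Changing 8.7 alone would leave the wider right in 8.8 to override it.

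- **8.7 and 8.8:** state that an investigator or sponsor decision prompted by adverse events or laboratory findings, including a decision to stop protocol PT, does not by itself end scheduled data collection. Treated children are asked to attend the remaining visits through week 12 unless consent is withdrawn.
- **9.3:** state that SAE reporting for every treated child, including early leavers, runs through week 12 (day 85) unless contact is refused.

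Clinical management stays with the investigator; only data collection changes. The cost is a few sentences in an amendment, some tracking of children who have stopped PT but remain in follow-up, visits already budgeted, and a week 12 contact for the few who cannot attend. It needs no additional patients or new procedures.
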